4.1.1 Pharmaceutical and Therapeutic Background

As treatment for HIV-1 has improved, HIV-1 infection has shifted from being an acute disease to being a chronic, manageable condition. There is now a clear medical need for new treatment regimens and dosing strategies that are both highly effective and very well tolerated. In particular, increased tolerability and ease of administration are expected to improve long-term adherence. A highly-potent nucleoside reverse transcriptase inhibitor (NRTI) with superior tolerability and ease of administration would be a valuable addition to the HIV-1 armamentarium.

MK-8583 is a novel, potent tenofovir prodrug (TFV PD) that belongs to the class of HIV-1 NRTIs. Marketed NRTIs include lamivudine, emtricitabine, abacavir, didanosine, stavudine, and zidovudine, as well as 2 TFV PDs, TDF and TAF.

TFV PDs have an acyclic nucleoside phosphonate on an adenine base. The phosphorylated moiety, TFV-DP competes with the natural substrate, deoxyadenosine, for incorporation by reverse transcriptase into newly synthesized cDNA strands. Once incorporated, TFV-DP terminates strand elongation, inhibiting viral replication.

TDF (VIREAD[®]) is a TFV PD, currently marketed by Gilead Sciences, Inc., that has been available since 2001. Following absorption, TDF is rapidly converted to TFV, which is then taken up by cells and converted intracellularly to the active anabolite, TFV -DP. After over 15 years in clinical use, TDF has been associated with small but significant decreases in kidney function (mean decrease in eGFR of 3.9 mL/ min, 95% confidence interval 2.1 - 5.7) [1] [2] and mild decreases in bone marrow density (BMD) [3], (approximate 2% loss in BMD in the spine and hip) in chronically treated patients. These effects are directly associated with high levels of TFV in circulation. TAF (VEMLIDY[®]), a more recently approved TFV PD, exhibits greater stability than TDF and is more efficiently taken up by target cells (i.e. PBMCs) thereby rendering lower levels of TFV in systemic circulation and lower levels of TFV available to cause toxicity to non-target cells (i.e. renal tubule cells and bone). The lower concentration of circulating TFV is believed to contribute to TAF's improved safety profile compared to TDF, although both compounds display similar efficacy in longer term clinical studies when administered as part of a complete treatment regimen.

Currently recommended first-line treatment of HIV infection in naïve patients calls for 3 agents and generally includes 2 NRTI agents in combination with either an integrase strand transfer inhibitor, a protease inhibitor, or a non-nucleoside reverse transcriptase inhibitor. While the currently approved NRTIs represent a cornerstone of modern ART, there are significant class associated toxicities including loss of bone mineral density, new or worsening renal impairment, severe lactic acidosis, and serious hypersensitivity reactions. Because tolerability issues are one of the most common reasons for lack of adherence and subsequent viral failure, a need exists for new, highly potent NRTIs, like MK-8583, with improved safety and tolerability. Furthermore, reducing the frequency that patients need to take anti-retroviral therapy from daily to weekly would remove a significant barrier to adherence and thereby improve health outcomes.

4.1.2 MK-8583

MK-8583 is a TFV PD that inhibits HIV-1 reverse transcriptase (RT). In vitro, MK-8583 demonstrated potent inhibition of HIV-1 R8 virus in PBMCs. TFV PDs are taken up by target cells and converted into TFV, which is then phosphorylated to the active antiviral TFV-DP. Extracellular TFV is also generated through prodrug metabolism and leakage out of target cells and must be renally cleared. Plasma TFV levels correlate with renal accumulation and toxicity. Therefore, prodrugs that are transported into leukocytes and converted to TFV-DP more readily will generate less plasma TFV and will have lower toxicity potential. In vitro, MK-8583 generates approximately 3-fold higher concentrations of intracellular TFV-DP than TAF. The more efficient conversion of MK-8583 into the active

metabolite leads to lower circulating levels of TFV, the metabolite responsible for toxicity, and therefore MK-8583 is expected to have a more favorable safety profile than TAF.

MK-8583 was evaluated in genetic toxicity assays, safety pharmacology models, and in repeat dose oral toxicity and toxicokinetic studies of up to 3 months in duration in rats and dogs. In both species, TFV was the major metabolite in plasma and excreta, which is consistent with in vitro studies that indicate hydrolysis to TFV is the primary elimination pathway of MK-8583.

MK-8583 is not expected to be a victim of CYP-mediated drug interactions. MK-8583 is a substrate of human P-gp and could be a victim of P-gp-mediated drug interactions. TFV is eliminated by renal excretion and is a substrate of OAT1, OAT3 and MRP4 in vitro. Therefore, TFV may be affected by drugs that reduce renal transport. In vitro, MK-8583 is an inhibitor of CYP3A, OATP1B1, and OATP1B3, and therefore MK-8583 has the potential to perpetrate drug interactions on substrates of these enzymes.

In preclinical safety studies, the primary toxicological effects of MK-8583 were noted in the gastrointestinal tract and in the kidneys. These changes were similar to those reported for other TFV PDs (TDF and TAF) at similar systemic exposures of the TFV metabolite. Based on the consistency of preclinical findings with MK-8583, TDF, and TAF, no specific preclinical findings were attributed to the novel prodrug, MK-8583.

MK-8583 was assessed in a single rising-dose study in healthy subjects. Following oral administration, MK-8583 was rapidly absorbed (time to maximum plasma concentration [T_{max}] ~ 0.5 hour) and rapidly eliminated from the plasma (terminal half-life [t_{1/2}] of 0.2 to 0.4 hours). Prodrug exposure was dose-proportional at doses ≥ 40 mg. Plasma TFV exposure was also dose-proportional, with a T_{max} of 1 to 4 hours and a t_{1/2} in the range of 19 to 30 hours. TFV-DP in PBMCs exhibited a median T_{max} of 4 to 24 hr and a terminal t_{1/2} ranging from 65 to 136 hours. The PBMC TFV-DP AUC increased approximately dose-proportionally, and the C_{max} increased somewhat more than dose-proportionally. Food somewhat lowered peak and extent of exposure of PBMC TFV-DP (GM fed/fasted ratio of 0.83 for AUC_{0-inf}, 0.32 for maximum concentration [C_{max}], 0.47 for C_{168hr}). Elimination of plasma MK-8583 was monophasic, while elimination of plasma TFV was biphasic. PBMC TFV-DP presented monophasic elimination, but showed signs of biphasic elimination at higher doses.

Single oral doses of MK-8583 up to 150 mg were generally well tolerated. No SAEs, events of clinical interest (ECIs), or deaths were reported. A total of 24 subjects enrolled in the trial. No trends were observed between AE incidence and increasing dose levels, and there were no AE findings consistent with renal or bone toxicity. No clinically meaningful trends were observed for changes in clinical laboratory values, vital signs (VS), or ECGs as a function of dose or treatment.

Please refer to the Investigator's Brochure (IB) for more detailed information on MK-8583.

4.2 Rationale

4.2.1 Rationale for the Trial and Selected Subject Population

MK-8583 has a promising preclinical and clinical profile and has potential to be an effective long acting TFV PD. This study is being conducted to assess the short-term anti-retroviral activity of MK-8583 monotherapy. Proof-of-concept trials demonstrate that agents that robustly suppress the VL as short-term monotherapy can be expected to deliver long-term efficacy as combination therapy [4]. This study's design and objectives conform to the EMA Guideline describing appropriate clinical development for anti-retroviral agents as monotherapy [5]. As described in this Guideline, the purpose of a monotherapy study is to characterize the relationship between dose, plasma concentration, and the short-term in vivo anti-retroviral activity.

Infected subjects who are therapy naïve will be enrolled in this study in order to decrease the presence of TFV resistant mutations. Prior to enrollment, subjects will be screened for the presence of common NRTI resistance mutations (International AIDS Society - USA (IASUSA) [6] to set a baseline standard for MK-8583-sensitivity to the viral variants present in each subject. Subjects identified with common mutations known to affect susceptibility to TFV (e.g., K65R, K70E, M184V/I, or combinations of three or more thymidine analog mutations (TAMs) including M41L, L210W, T215Y, D67N, K70R, K219Q/E/N) will be excluded from the study. Should unanticipated non-responders or viral breakthrough be observed despite this pre-screening process, a portion of the screening blood sample will be archived for phenotyping and/or genotyping of any previously unidentified clinically meaningful resistance variants.

4.2.2 Rationale for Dose Selection/Regimen/Modification

As this is a Phase I assessment of MK-8583 in humans, and the PK, PD and safety profiles of the compound are still being evaluated, modifications to the dose or dosing regimen may be required to achieve the scientific goals of the trial objectives and/or to ensure appropriate safety monitoring of the trial subjects. Details of allowed modifications are provided in Section 7.1.5.5 - Trial Design/Dosing/Procedures Modifications Permitted within Protocol Parameters.

The doses tested in this study will evaluate the effectiveness of MK-8583 in suppressing viral replication and will allow for assessment of potential differentiation in tolerability and efficacy. The study is specifically designed with an emphasis on collecting single dose viral dynamic data. Since only a single dose of MK-8583 will be administered to each subject, risk of resistant strain emergence is minimal.

Doses selected for this study are projected to fall within the expected clinical dose range. A dose that achieves a TFV-DP C168h in PBMCs of 100 nM is projected to be efficacious. This is approximately the Day 7 PBMC Ctrough achieved with daily dosing of TDF 300 mg (the therapeutic dose) for one week, which results in a 0.5 log₁₀ reduction in VL [4]. In the single-rising dose study of MK-8583 in healthy subjects, a PBMC TFV-DP C168h target of 100 nM was achieved at doses ≥ 40 mg of MK-8583.

To maximize the chances of efficacy and minimize the impact of inter-subject PK variability, a 100 mg dose of MK-8583 will be administered to subjects in Panel A. This dose is expected to achieve PBMC TFV-DP concentrations well above that of the projected minimum effective dose of 40 mg (see above) while maintaining a plasma concentration of the TFV metabolite (the relevant correlate of toxicity) at $\leq \frac{1}{2}$ the exposure seen at the preclinical no-observed-adverse-effect level (NOAEL).

There will be a break between dosing of panels to allow for review of all available safety, PK, and viral dynamic data to inform dose selection in the following panel. It is estimated that this review will take approximately 30-40 days. Because plasma MK-8583, plasma TFV, and PBMC TFV-DP PK data from healthy subjects are expected to be similar to that of HIV-1 infected subjects, PK data from single doses administered to healthy subjects in Protocol 001 will also be used to aid in the selection of doses for the present study to ensure that plasma MK-8583 levels do not exceed the exposure cap.

The specific dose selected for Panel B will depend on data from Panel A. Assuming PK data indicate that higher exposures maintain safety margins, a higher dose may be tested to see if it delivers greater efficacy. Alternatively, if 100 mg generates exposures in HIV-infected subjects that are higher than what was seen in healthy subjects, or if safety concerns arise, a lower dose may be tested. After Panel B, the Sponsor will assess the utility of testing a third dose in Panel C to further explore PK, PD, and the safety profile of the compound.

Additionally, safety data through at least 168 hours post-dose, including AEs, standard laboratory safety tests, VS, and 12-lead ECGs, physical examinations (PEs) will be reviewed by the Sponsor and the investigator prior to dose escalation, and the decision to proceed to a new dose level will be based upon acceptable safety of MK-8583 at the previous dose. The doses selected for Panels B and C in this study will not exceed the maximum dose of 150 mg previously administered to healthy subjects.

The reduction in VL for each dose level will be compared to historical placebo data from clinical trials previously conducted by the Sponsor. Given the overall favorable safety profile of MK-8583 in preclinical and clinical testing to date, a placebo control to minimize investigator and subject bias with respect to adverse experiences is not deemed necessary.

4.2.2.1 Starting Dose for This Trial

The proposed starting dose in Panel A is 100 mg as noted above. Prior clinical evaluation up to 150 mg demonstrated that MK-8583 was generally well tolerated.

The toxicity studies (summarized below) indicated that the no-observed-adverse-effect level (NOAEL) in the more sensitive preclinical species was 3 mg/kg/day in the dog. Previous studies indicate TFV PDs exhibit generally similar PK in healthy subjects and HIV-infected subjects [7]. Assuming the same correlation holds for MK-8583, a dose of 100 mg is expected to yield an AUC_{0-inf} (approximately equivalent to AUC_{0-168hr}) for plasma TFV and plasma MK-8583 of 2,380 nM*hr and 430 nM*hr, respectively. The dog NOAEL yielded an AUC_{0-168hr} (calculated by multiplying the AUC_{0-24hr} x 7 days) for TFV and MK-8583 of 17,850 nM*hr and 620 nM*hr, respectively. Therefore, relative to the predicted exposures at 100 mg, the safety data provide a 7.5-fold (for TFV) and 1.4-fold (for MK-8583) safety margin (see [Table 2](#)).

Table 2 Exposure predictions for the starting dose of 100 mg

	Preclinical NOAEL AUC0-168hr (nM*hr) ^a	Clinical Dose	Clinical AUC0- inf (nM*hr)	Exposure Multiple
Plasma TFV	17,850	100 mg	2,380 ^b	7.5
		150 mg	3,840 ^c	4.7
Plasma MK-8583	620	100 mg	430 ^b	1.4
		150 mg	684 ^c	0.9
^a AUC0-168hr (AUC0-24 x 7 days) observed at the dog NOAEL (3 mg/kg/day) ^b AUC0-inf interpolated from Protocol 001, assuming dose-proportionality ^c AUC0-inf calculated from Protocol 001, predicted to be similar to AUC0-168hr				

4.2.2.2 Maximum Dose/Exposure for This Trial

The maximum allowable clinical exposure for this study is defined by the safety findings from 3-month Good Laboratory Practice (GLP) oral toxicity studies in rat and canine models.

In rats, the 3-month oral toxicity study identified no test article related toxicology findings at the highest dose tested, 150 mg/kg/day, and this was set as the rodent no-observed-adverse-effect level (NOAEL).

Dogs were administered MK-8583 at 3, 10, and 30 mg/kg/day in 3-month oral toxicity studies. All animals in the 30 mg/kg/day dose group were terminated early in Study Week 7 or 8 due to severe body weight losses, associated with decreased food consumption, decreased activity, and decreased heart rate. Increased incidences of emesis and salivation, and hematological and serum biochemical changes were also observed, including laboratory and histomorphologic indicators of significant kidney toxicity. In the 10 mg/kg/day dose group, observed test article-related clinical pathology findings included mild increases in creatinine associated with histomorphologic changes in the kidneys and slight increases in aspartate aminotransferase (AST) and alkaline phosphatase. The increases in AST and alkaline phosphatase were not associated with histomorphologic changes and were therefore not toxicologically significant. The maximum tolerated dose for the dog was therefore set at 10 mg/kg/day.

Test article-related postmortem changes were observed in the stomachs of dogs receiving the 3 mg/kg/day dose. Specifically, these were large vacuolated cells in the gastric mucosal pyloric mucosa. Although these changes were of unknown toxicological significance, the NOAEL for the dog was set at 3 mg/kg/day.

There are significant differences in the protein binding of MK-8583 in rat (71-82%, depending on concentration) vs. human and dog (93% and 95%, respectively), whereas TFV protein binding is minimal across all species. For these reasons, exposure to total TFV and exposure to unbound MK-8583 were used to select the more sensitive species for the NOAEL exposure margins.

The AUC_{0-168hr} was selected as the relevant exposure parameter, instead of C_{max}, because the preclinical toxicity of MK-8583 was associated with chronic dosing and was similar to clinical toxicity observed with chronic dosing of marketed TFV prodrugs. (The mean TFV C_{max} at the preclinical NOAEL and at the maximum clinical dose of 150 mg were 102 nM and 175 nM, respectively. The mean MK-8583 C_{max} at the preclinical NOAEL and at the maximum clinical dose of 150 mg were 168 nM and 1,074 nM, respectively.)

TFV Exposure Multiple: Comparing the TFV AUC_{0-168hr} at the dog NOAEL (17,850 nM*hr at 3 mg/kg/day) to that of the rat (446,000 nM*hr at 150 mg/kg/day), the dog represents the more sensitive species. Therefore, the maximum allowable exposure is based on the TFV AUC_{0-168hr} at the NOAEL of the dog, in this case 17,850 nM*hr. In healthy subjects, the maximum dose of 150 mg yielded a TFV AUC_{0-inf} (approximately equal to the AUC_{0-168hr}) of 3836 nM*hr; the preclinical safety data provide a 4.7-fold exposure margin (EM) (see [Table 2](#)).

MK-8583 Exposure Multiple: Whereas the plasma protein binding of TFV is minimal across all species, there are significant inter-species differences in the protein binding of MK-8583 (~70-80% in rat, ~93-95% in human and dog). The total MK-8583 AUC_{0-168hr} at the dog NOAEL (620 nM*hr at 3 mg/kg/day) and at the rat NOAEL (540 nM*hr at 150 mg/kg/day) are similar. But comparing the unbound MK-8583 AUC_{0-168hr} at the dog NOAEL (29.8 nM*hr at 3 mg/kg/day) to that of the rat (96.6 nM*hr) identifies the dog as the more sensitive species. In healthy subjects, the maximum dose of 150 mg yielded an MK-8583 AUC_{0-inf} (approximately equal to the AUC_{0-168hr}) of 684 nM*hr, which is 0.9-fold that of the MK-8583 AUC at the dog NOAEL (620 nM*hr, see [Table 2](#)).

All changes observed in the toxicology studies were similar to those reported for other TFV prodrugs (TDF and TAF) at similar systemic exposures of the TFV metabolite [8] and [9]. Based on the consistency of preclinical findings with MK-8583, TDF, and TAF, no specific preclinical findings were attributed to the novel prodrug, MK-8583. Therefore, although the MK-8583 prodrug exposure at 150 mg slightly exceeds that at the preclinical NOAEL, the 150 mg dose is an appropriate maximum for this single-dose trial because the observed preclinical toxicity is attributable to TFV, not to the MK-8583 prodrug, and because 150 mg was generally well-tolerated by healthy subjects in Protocol 001.

While plasma MK-8583, plasma TFV, and PBMC TFV-DP PK data from healthy subjects are expected to be similar to that of HIV-1 infected subjects, the PK and safety data from each panel in this study will also be reviewed and compared with data from Protocol 001 prior to dose selection for the next panel.

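### MK-8583 margins are stated on total AUC only; on unbound AUC, the basis used to choose the NOAEL species, the margin is about 1.0 at 100 mg and 150 mg is about 1.6 times the dog NOAEL

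*Combined protocol and SAP*

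**What the plan says.** Section 4.2.2.2 explains that protein binding of MK-8583 differs between species and that "exposure to total TFV and exposure to unbound MK-8583 were used to select the more sensitive species for the NOAEL exposure margins". It gives binding in "human and dog (93% and 95%, respectively". It finds the total AUCs at the dog and rat NOAELs similar (620 and 540 nM·hr) and settles the choice of species by comparing the unbound AUC "at the dog NOAEL (29.8 nM*hr at 3 mg/kg/day) to that of the rat (96.6 nM*hr".

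The margins are then stated on total AUC. Section 4.2.2.1 says that "relative to the predicted exposures at 100 mg, the safety data provide a 7.5-fold (for TFV) and 1.4-fold (for MK-8583) safety margin", and Table 2 prints MK-8583 multiples of 1.4 at 100 mg and 0.9 at 150 mg. For 150 mg, Section 4.2.2.2 gives "684 nM*hr, which is 0.9-fold that of the MK-8583 AUC at the dog NOAEL". Its closing paragraphs accept the dose "although the MK-8583 prodrug exposure at 150 mg slightly exceeds that at the preclinical NOAEL", because the toxicity seen in animals is attributed to TFV and because healthy subjects tolerated 150 mg. No unbound human AUC and no unbound margin appear anywhere.

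**The concern.** The protocol changes its exposure measure between two steps of one argument. Unbound drug decides which animal sets the reference, and total drug then decides how far the clinical dose lies from it. The change would be harmless if dogs and humans bound MK-8583 to the same degree. By the protocol's figures they do not: about 5% is unbound in the dog and 7% in humans. A total-AUC comparison therefore flatters the human dose.

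What is at stake is the accuracy of a stated safety figure. Investigators and ethics committees read that the dose for all Panel A subjects has a 1.4-fold prodrug margin and that the highest permitted dose is slightly over the NOAEL exposure. One sentence, read alone, even places 150 mg below the NOAEL.

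**Working it through.** **Inputs.** From Section 4.2.2.2: dog NOAEL total AUC 620 nM·hr; dog NOAEL unbound AUC 29.8 nM·hr; human binding 93%; total AUC at 150 mg 684 nM·hr. From Section 4.2.2.1 and Table 2: predicted total AUC at 100 mg 430 nM·hr.

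**Step 1: the protocol's multiples.** Multiple = NOAEL AUC / clinical AUC, both total.
- 100 mg: 620/430 = 1.44, printed as 1.4.
- 150 mg: 620/684 = 0.91, printed as 0.9.

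Table 2 reproduces.

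**Step 2: the sentence on 150 mg.** It describes 684 as a multiple of 620. That is 684/620 = 1.10. The printed 0.9 is the reciprocal, 620/684.

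**Step 3: unbound fractions.** Dog: 29.8/620 = 0.048, in line with 95% binding. Human: 1 − 0.93 = 0.07.

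**Step 4: unbound multiples.** Unbound clinical AUC = total AUC × 0.07.
- 100 mg: 430 × 0.07 = 30.1 nM·hr; 29.8/30.1 = 0.99.
- 150 mg: 684 × 0.07 = 47.9 nM·hr; 29.8/47.9 = 0.62, or 47.9/29.8 = 1.61 times the NOAEL.

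As a cross-check, the unbound multiple is the total multiple times the ratio of unbound fractions, 0.0481/0.07 = 0.687. This gives 1.44 × 0.687 = 0.99 and 0.91 × 0.687 = 0.62.

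**Step 5: sensitivity to binding.** A printed 93% may stand for 92.5% to 93.5%. The dog unbound AUC is taken as stated (29.8) or as exactly 5% of 620 (31.0). The human values of 94% and 95% are assumptions, added to show how far the result depends on this input.

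| Human binding | Dog unbound AUC (nM·hr) | Multiple at 100 mg | 150 mg relative to NOAEL |
|---|---|---|---|
| 92.5% | 29.8 | 0.92 | 1.72 |
| 93% | 29.8 | 0.99 | 1.61 |
| 93.5% | 29.8 | 1.07 | 1.49 |
| 93% | 31.0 | 1.03 | 1.54 |
| 93.5% | 31.0 | 1.11 | 1.43 |
| 94% (assumed) | 29.8 | 1.16 | 1.38 |
| 95% (assumed) | 29.8 | 1.39 | 1.15 |

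The stated 1.4 is recovered on an unbound basis only if human binding is about equal to dog binding.

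**The case against.** The strongest reply is that this is a choice of basis, not a miscalculation. The two Table 2 multiples are right on total AUC. The protocol says that unbound exposure served to choose the species, and the contrast that drove this was the rat (71% to 82% bound) against human and dog, which a later paragraph of Section 4.2.2.2 groups together at about 93% to 95%. The unbound result turns on a two-point binding difference whose assay error is not given, and at 100 mg the range crosses 1. All of that stands. It calls for presenting the unbound figures with a caveat. It is not a reason to leave them out, since the same section assigns 93% and 95% to the two species separately and treats unbound exposure as the relevant comparison.

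It is also fair that prodrug exposure is not hidden. Section 4.2.2.2 reports a mean MK-8583 Cmax of 1,074 nM at 150 mg against 168 nM at the NOAEL, a ratio of 6.4, and admits the AUC exceedance. But the protocol sets Cmax aside in favour of AUC, so the AUC comparison should be complete.

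Three stronger readings are tempting, and the documents do not support them.

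- **That 100 mg rests on the 1.4-fold margin alone.** Section 4.1.2 names TFV as the metabolite responsible for toxicity. Section 4.2.2 supports 100 mg by keeping plasma TFV at no more than half its NOAEL exposure. Section 4.2.2.1 opens with tolerability up to 150 mg, and the end of Section 4.2.2.2 attributes no animal finding to the prodrug at any dose.
- **That a dose is unsafe.** The TFV margins do not change, the reference comes from a three-month daily study while subjects receive one dose, and 150 mg has already been given to healthy subjects.
- **That a numerical prodrug limit, say 684 nM·hr, is needed** because Section 4.2.2 speaks of using Protocol 001 data "to ensure that plasma MK-8583 levels do not exceed the exposure cap" without giving an MK-8583 value. The 150 mg ceiling, the TFV limit of 17,850 nM·hr, the comparison with Protocol 001 before each panel and the joint dose decision already operate. A limit on prodrug exposure would also restrict dose on a quantity to which the protocol attributes no toxicity.

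**Conclusion.** The point holds as a correction to stated figures. On unbound MK-8583 the margin at 100 mg is about 1.0 (0.92 to 1.07 under rounding of the human binding value), against the stated 1.4. The supportable statement at 100 mg is that there is essentially no unbound prodrug margin, not that the NOAEL is exceeded. At 150 mg, unbound exposure is about 1.6 times the dog NOAEL (1.5 to 1.7), against 1.1 times on total AUC. Calling this slight understates the unbound exceedance. The ratio in the 150 mg sentence is inverted whichever basis is used.

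The unbound values assume that the printed binding percentages apply at the concentrations concerned and that predicted exposures in HIV-infected subjects match Protocol 001, as the protocol itself assumes. If human binding were really 94% or 95%, the gap would narrow, but 150 mg would still exceed the unbound NOAEL. The TFV margins of 7.5 and 4.7 and the rationale for both doses are untouched.

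**What to change.** 1. Add unbound MK-8583 rows to Table 2: NOAEL 29.8 nM·hr; 100 mg, 30.1 nM·hr, multiple 1.0; 150 mg, 47.9 nM·hr, multiple 0.6. Add a footnote giving the binding values used and saying that the multiples depend on their precision.
2. In Section 4.2.2.1, state the MK-8583 margin as 1.4-fold on total and about 1.0-fold on unbound MK-8583.
3. In Section 4.2.2.2, change the 150 mg comparison to 1.1-fold the dog NOAEL AUC (about 1.6-fold unbound), and put the same two figures in place of the wording that the exceedance is slight.

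These are text changes. No dose, eligibility criterion, stopping rule or analysis is altered. The price is a less favourable prodrug figure in the dose rationale.
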